### **7.6.8.3 Time-to resolution of IMAE**

Time to resolution of the following specific events will be summarized separately for each category/subcategory.

- Time-to resolution of any grade IMAE
- Time-to resolution of grade 3 to 5 IMAE

Time-to resolution analyses are restricted to treated subjects who experienced the specific events. Time-to resolution where immune modulating medication was initiated analyses is restricted to treated subjects who experienced the specific events and who received immune modulating medication during the longest IMAE.

The following summary statistics will be reported: percentage of subjects who experienced the specific events, percentage of subjects with resolution of the longest IMAE, median time-to resolution along with 95% CI (derived from Kaplan-Meier estimation) and ranges.

See time-to resolution definition subsection of [Appendix 1](#) for additional details.

The analyses will be conducted using the 100-day safety window.

### **7.6.8.4 Immune modulating medication for IMAE**

For each category of IMAE, the following will be reported for each treatment group:

- Percentage of subjects who received immune modulating concomitant medication for management of other events of special interest in the category among subjects who experienced at least one other events of special interest in the category.
- The total medication treatment duration, duration of high dose of corticosteroid and tapering duration (summary statistics)

These analyses will be performed on any IMAE, grade 3-5 IMAE.

The analysis will be conducted using the 100-day safety window.

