### **6.2.2 Adverse Events of Interest**

IMAEs are specific events occurring within 100 days of the last dose of study drug (which includes pneumonitis, diarrhea/colitis, hepatitis, nephritis/renal dysfunction, rash, and endocrine abnormalities [adrenal insufficiency, hypothyroidism/thyroiditis, hyperthyroidism, diabetes mellitus, and hypophysitis]), regardless of causality, for which subjects received immunosuppressive medication for treatment of the event. The exception to the immunosuppressive medication criteria for IMAEs is endocrine events

(hypothyroidism/thyroiditis, hyperthyroidism, hypophysitis, diabetes mellitus, adrenal insufficiency), which are included regardless of treatment since these events are often managed without immunosuppression.

Per FDA guidance, IMAE analyses included events, regardless of causality, occurring within 100 days of the last dose. These analyses are limited to subjects who received immunosuppressive medication for treatment of the event, with the exception of endocrine events (hypothyroidism/thyroiditis, hyperthyroidism, hypophysitis, diabetes mellitus, adrenal insufficiency), which were included in the analysis regardless of treatment since these events are often managed without immunosuppression.

Table 6.2.2-1 provides a summary of the IMAEs category and their respective PTs.

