### **7.6.8 Immune Mediated Adverse Events**

IMAEs are specific events occurring within 100 days of the last dose of study drug (which includes pneumonitis, diarrhea/colitis, hepatitis, nephritis/renal dysfunction, rash, and endocrine abnormalities [adrenal insufficiency, hypothyroidism/thyroiditis, hyperthyroidism, diabetes mellitus, and hypophysitis]), regardless of causality, for which subjects received immunosuppressive medication for treatment of the event. The exception to the immunosuppressive medication criteria for IMAEs is endocrine events (hypothyroidism/thyroiditis, hyperthyroidism, hypophysitis, diabetes mellitus, adrenal insufficiency), which are included regardless of treatment since these events are often managed without immunosuppression.

Unless otherwise specified, analyses will be performed by IMAE category on events where immune modulating medication was initiated. Analyses may also be repeated by categories of endocrine events.

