### **7.6.8.2 Time-to onset of IMAE**

Time-to onset of the following specific events will be summarized for each category of IMAEs:

- Time-to onset of any grade IMAE
- Time-to onset of grade 3 to 5 IMAE
- Time-to onset of any grade IMAE where immune modulating medication was initiated
- Time-to onset of grade 3 to 5 IMAE where immune modulating medication was initiated

The following summary statistics will be reported for treated subjects who experienced at least one immune-mediated adverse event from the category: median, min and max. Median time to onset along with 95% confidence interval using the Kaplan-Meier technique is also reported for all treated subjects. If the subject did not experience a IMAE in the category, time-to onset will be censored at the maximum follow-up time of all subjects in their respective treatment group (i.e. for subjects without an event, follow-up time is defined from first dosing date up to last dosing date +100 days if subjects are off treatment and followed for at least 100 days, otherwise it is defined up to the last known alive date).

See time-to onset definition subsection of [Appendix 1](#) for additional details. The analyses will be conducted using the 100-day safety window.

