#### **7.6.11.4 Immune Modulating Medication for other events of special interest**

For each category of other events of special interest, the following will be reported for each treatment group:

- Percentage of subjects who received immune modulating concomitant medication for management of other events of special interest in the category among subjects who experienced at least one other events of special interest in the category.
- The total medication treatment duration, duration of high dose of corticosteroid and tapering duration (summary statistics)

These analyses will be performed on any other events of special interest, grade 3-5 other events of special interest.

The analysis will be conducted using the 100-day safety window.

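### SAP 7.6.8.4 defines its IMAE medication percentage on the wrong event type, and rewording it to IMAE gives essentially 100% by definition in the five non-endocrine categories

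*SAP*

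**What the plan says.** SAP 7.6.8.4 is headed and introduced as an IMAE section, and it closes: "These analyses will be performed on any IMAE, grade 3-5 IMAE". Its percentage bullet reads "Percentage of subjects who received immune modulating concomitant medication for management of other events of special interest in the category among subjects who experienced" such an event. The bullet in SAP 7.6.11.4, which does belong to other events of special interest, has the same wording: "for management of other events of special interest in the category among subjects who experienced at least one other events of special interest". SAP Appendix 1 names IMAEs, select AEs and other events of special interest as distinct kinds of adverse event of interest.

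The IMAE definition in SAP 7.6.8 covers listed events up to 100 days after last dose, "regardless of causality, for which subjects received immunosuppressive medication for treatment of the event". Endocrine events are exempt from the medication condition. Protocol 6.2.2 has the same rule: "These analyses are limited to subjects who received immunosuppressive medication for treatment of the event, with the exception of endocrine events".

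SAP 7.6.8 also sets a default: "Unless otherwise specified, analyses will be performed by IMAE category on events where immune modulating medication was initiated". It adds: "Analyses may also be repeated by categories of endocrine events".

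The secondary endpoint in SAP 4.2 includes the percentage of subjects given immune modulating medication or hormonal replacement. It is analysed in SAP 7.6.2, which correctly names high-grade IMAEs.

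**The concern.** There are two problems, and solving the first exposes the second.

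First, numerator and denominator both name an event type that the section is not about. A programmer who follows the bullet produces a table under an IMAE title that counts other subjects and other events.

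Second, the natural repair is to write IMAE in both places. For non-endocrine events, though, medication is part of what makes the event an IMAE. The percentage medicated then restates the inclusion rule. A reader of the clinical study report could take 100% for pneumonitis or rash as a finding about how often such events needed treatment.

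The secondary objective is to characterise the outcome of high-grade IMAEs, and this table is part of the description of how they were managed.

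**Working it through.** The plan gives no figure for this percentage, so there is nothing to reproduce. The check is on the definitions.

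**Step 1: which events are named.**

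| Place | Section is about | Percentage bullet names |
|---|---|---|
| SAP 7.6.8.4 | IMAE | other events of special interest |
| SAP 7.6.10.4 | select AE | select AE |
| SAP 7.6.11.4 | other events of special interest | other events of special interest |

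Only 7.6.8.4 is mismatched. The SAP document history says version 2.0 modified the IMAE section and added the section on other events, which fits text carried across. The second bullet of 7.6.8.4 (durations) names no event type, so the error is confined to the percentage.

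**Step 2: the percentage after rewording to IMAE.** For a non-endocrine category, let n be the treated subjects with a listed event in the window, and q the share of them given immunosuppressive medication for it.

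- Subjects with an IMAE in the category (denominator): q × n, because the definition keeps only medicated events.
- Of these, medicated (numerator): q × n.
- Percentage: (q × n) / (q × n) = 100% for any q above 0, for any grade and for Grade 3-5.

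For an endocrine category the denominator is n, so the percentage is (q × n) / n = q and can vary.

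The documents do not give q. With assumed values:

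| Assumed q | Non-endocrine, IMAE-based | Endocrine, IMAE-based | Any category, before the medication criterion |
|---|---|---|---|
| 0.2 | 100% | 20% | 20% |
| 0.5 | 100% | 50% | 50% |
| 0.8 | 100% | 80% | 80% |

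A simulation of 5,000 subjects per category, with an assumed event probability of 0.1, agreed. It gave 100.0% in all five non-endocrine categories at each q. The endocrine categories gave 18.5-20.7%, 49.5-53.2% and 78.5-82.2%.

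**Step 3: how many categories.** Protocol Table 6.2.2-1 has ten. Five are non-endocrine: pneumonitis, diarrhea/colitis, hepatitis, nephritis and renal dysfunction, and rash. Five are endocrine: adrenal insufficiency, hypothyroidism/thyroiditis, hyperthyroidism, hypophysitis and diabetes mellitus. The percentage is fixed in 5/10 = 50% of categories. Appendix 1 uses the sponsor's list current at analysis, so the count may change.

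**Step 4: two conditions on the 100%.**

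- The definition speaks of immunosuppressive medication, the percentage of immune modulating medication. The SAP does not equate them. Its examples of the latter in 4.2 include corticosteroids, infliximab and mycophenolate mofetil, which supports treating one as covering the other.
- SAP 7.4.3 limits concomitant medication to 100 days after last dose, while the IMAE definition puts no time limit on the medication. An event on day 95 first treated on day 105 would be in the denominator and not the numerator. This should be rare.

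**Step 5: related summaries.** SAP 7.6.2 has the same circularity for non-endocrine events among subjects with high-grade IMAEs. SAP 7.6.10.4 gives a medicated percentage for select AEs with no stated medication criterion, but in the 30-day window, so it is only a partial substitute for the 100-day IMAE table.

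**The case against.** The strongest reply is that the intent is plain. The heading, lead-in and closing line of 7.6.8.4 all say IMAE, the endpoint itself is analysed correctly in 7.6.2, and SAP section 9 leaves the full list of analyses to a Data Presentation Plan that is not available here. The medication criterion is also deliberate: protocol 6.2.2 attributes the approach to FDA guidance, and the definition opens the parent SAP section.

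Much of this stands. It is not known that any table would carry the wrong events, and the IMAE definition is not a defect. But the bullet is the only statement of numerator and denominator in that section, and it is wrong as written. A deliberate definition also does not make a percentage conditioned on it informative.

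Three stronger readings are tempting and are not supported.

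- **That all categories are fixed at 100%.** A reader might infer this from the 7.6.8 default. The default yields where a section specifies otherwise, and 7.6.8.4 arguably does so by naming any IMAE. Section 7.6.8.2 lists onset times both without the restriction and with it ("Time-to onset of grade 3 to 5 IMAE where immune modulating medication was initiated"), so the default is not applied uniformly. The text needs a clarifying sentence; it does not establish the result.
- **That the pooled 7.6.2 percentage falls below 100% only through subjects with endocrine events alone.** Section 7.6.2 also refers to all subjects in Groups 1, 2 and 3, which read literally includes subjects with no IMAE. SAP 4.1 lists neurologic events, for which 7.6.8 gives no category or medication rule. No bound on the pooled figure follows.
- **That the share of categories or preferred terms measures the share of subjects affected.** The documents do not say how events will distribute across categories.

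**Conclusion.** The point holds at minor severity. Confidence is high on the wrong event type and on the circularity of the non-endocrine percentages. Followed literally, 7.6.8.4 tabulates the wrong events. Corrected to IMAE, it returns essentially 100% in five of ten categories regardless of how often events were treated, under the two conditions in Step 4 of the working. Rewording alone is therefore not enough.

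This is a descriptive secondary summary. The primary endpoint, the percentage receiving at least 40 mg prednisone equivalents, the medication durations and the resolution summaries do not depend on it.

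**What to change.** 1. In SAP 7.6.8.4, replace other events of special interest with IMAE in both places, and state that the medication-initiated default of 7.6.8 does not apply to this percentage.
2. Keep the IMAE-based percentages as planned, with a footnote that the non-endocrine categories are 100% by definition. Note in 7.6.2 that non-endocrine IMAEs enter as medicated by definition, without stating a bound for the pooled figure.
3. Add a supplementary percentage medicated, for any grade and for Grade 3-5. Its denominator is treated subjects with an event in the Table 6.2.2-1 preferred terms (or the list current at analysis) within 100 days of last dose, before the medication criterion is applied.

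Items 1 and 2 are text changes. Item 3 uses data already planned: adverse events are collected for at least 100 days after last dose (protocol 6.2.1) and concomitant medications are summarised to 100 days (SAP 7.4.3). It needs some extra programming, including linking each medication to its event. Its denominator will take in events of other cause, such as diarrhea or raised creatinine, and will not match the IMAE count, so it needs its own footnote. The protocol's endpoint is unchanged, so no protocol amendment is needed.

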##### 4.2 Secondary Endpoint(s)

The secondary objective of the study will be assessed by measuring the following:

- median time to onset, median time to resolution of high grade (Grade 3-4 and Grade 5) IMAEs
- percentage of subjects who received immune modulating medication (e.g. corticosteroids, infliximab, cyclophosphamide, Intravenous Immune Globulin [IVIG], and mycophenolate mofetil), or hormonal replacement therapy, the percentage of subjects who received  $\geq 40$  mg prednisone equivalents, total duration of all immune modulating medications given for the IMAE and summary of subjects with resolution of AEs after initiating these therapies.

█ [REDACTED]

█ [REDACTED]

█ [REDACTED]

█ [REDACTED]

[REDACTED]

[REDACTED]

[REDACTED]

[REDACTED]

[REDACTED]

[REDACTED]

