## **7 STATISTICAL ANALYSES**

### **7.1 General Methods**

Unless otherwise noted, the bulleted titles in the following subsections describe tabulations of discrete variables, by the frequency and proportion of subjects falling into each category. Percentages given in these tables will be rounded and, therefore, may not always sum to 100%. Continuous variables will be summarized using the mean, standard deviation, median, minimum and maximum values.

Time to event distribution will be estimated using Kaplan Meier techniques. This will be done for endpoints PFS-1, OS and DOR. Median survival time along with 95% CI will be constructed based on a log-log transformed CI for the survivor function  $S(t)^{4,5}$ . Rates at fixed time points will be derived from the Kaplan Meier estimate and corresponding confidence interval will be derived based on Greenwood formula for variance derivation and on log-log transformation applied on the survivor function  $S(t)^7$ .

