### 7.4.1 Administration of Study Therapy

The following parameters will be summarized (descriptive statistics) by treatment arm:

- Relative dose intensity (%) using the following categories: < 50%; 50 - < 70%; 70 - < 90%; 90 - < 110%; ≥ 110%.
- Number of doses received (summary statistics)
- Cumulative dose
- Duration of treatment: duration of treatment will be presented using a Kaplan-Meier curve whereby the last dose date will be the event date for subjects who discontinued study therapy. Subjects who are still on study therapy will be censored on their last dose date.

A by-subject listing of extent of exposure: weight, number of doses, date of first and last dose, cumulative dose, relative dose intensity, duration of treatment, and reason for discontinuation

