### **7.6.2 Secondary Analyses**

Additional descriptive statistics will include median values using the Kaplan-Meier (KM) product-limit method with 95% CI using Brookmeyer and Crowley of time to onset and time to resolution of IMAEs, and will be presented for all treated subjects in Groups 1, 2, and 3. Time to onset is calculated from first dosing date to the event onset date. If a subject never experienced the given AE, the subject will be censored at the last contact date. Time to resolution is calculated from the AE onset date to AE end date. If an AE is ongoing at the time of analysis, the time to resolution will be censored at the last contact date.

Management of high-grade (CTCAE v4.0 Grade 3-4 and Grade 5) IMAEs will be characterized by measuring percentage of subjects who received immune modulating medication (or hormonal replacement therapy), percentage of subjects who received  $\geq 40$  mg prednisone equivalents, and total duration of all immune modulating medications given for the event, in all treated subjects who have experience high-grade (CTCAE v4.0 Grade 3-4 and Grade 5) IMAEs and all subjects in Groups 1, 2, and 3.

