## 8 CONVENTIONS

The following conventions may be used for imputing partial dates for analyses requiring dates:

For missing and partial adverse event onset dates, imputation will be performed using the Adverse Event Domain Requirements Specification. Missing and partial Non-Study Medication Domain dates will be imputed using the derivation algorithm described in BMS Non-Study Medication Domain Requirements Specification.

For death dates, the following conventions will be used for imputing partial dates:

- If only the day of the month is missing, the 1st of the month will be used to replace the missing day. The imputed date will be compared to the last known alive date +1 day and the maximum will be considered as the death date.
- If the month or the year is missing, the death date will be imputed as the last known alive date + 1 day
- If the date is completely missing but the reason for death is present the death date will be imputed as the last known alive date + 1 day

For date of progression, the following conventions will be used for imputing partial dates:

- If only the day of the month is missing, the 1st of the month will be used to replace the missing day.

- If the day and month are missing or a date is completely missing, it will be considered as missing.
- \* In case, the date of death is present and complete, the imputed progression date will be compared to the date of death. The minimum of the imputed progression date and date of death will be considered as the date of progression.

The following conversion factors will be used to convert days to months or years: 1 month = 30.4375 days and 1 year = 365.25 days.

Duration (e.g. time from first diagnosis of NSCLC to first dosing date, duration response, and time to response) will be calculated as follows:

Duration = (Last date - first date + 1)

All statistical analyses will be carried out using SAS (Statistical Analysis System software, SAS Institute, North Carolina, USA) unless otherwise noted.

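### Durations of immune-modulating medication are given as plain summary statistics with no rule for courses still ongoing, so the mean, and sometimes the median, can come out too low

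*SAP*

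**What the plan says.** **The endpoint.** SAP 4.2 lists, within the secondary endpoint, "total duration of all immune modulating medications given for the IMAE and summary of subjects with resolution of AEs after initiating these therapies". SAP 7.6.2 repeats the item as "total duration of all immune modulating medications given for the event" and gives no estimator and no rule for open courses.

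**The method.** SAP 7.6.8.4 lists three durations, in the 100-day window: "The total medication treatment duration, duration of high dose of corticosteroid and tapering duration (summary statistics". The general rule in SAP 7.1 is "Continuous variables will be summarized using the mean, standard deviation, median, minimum and maximum values". The Kaplan-Meier sentence in the same section reads "This will be done for endpoints PFS-1, OS and DOR"; medication duration is not named. The same summary-statistics line recurs in SAP 7.6.10.4 (select AEs) and 7.6.11.4 (other events of special interest).

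**Neighbouring analyses.** For resolution of the same events, SAP 7.6.2 says "If an AE is ongoing at the time of analysis, the time to resolution will be censored at the last contact date". For nivolumab duration, SAP 7.4.1 uses Kaplan-Meier and says "Subjects who are still on study therapy will be censored on their last dose date".

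**Dates.** SAP section 8 says "Missing and partial Non-Study Medication Domain dates will be imputed using the derivation algorithm described in BMS Non-Study Medication Domain Requirements Specification". That specification is not among the documents.

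**The concern.** A course that has not stopped has a right-censored length: only a lower bound is known. Open courses are realistic here for three reasons.

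- The SAP's schedule of analyses allows data cuts for publication before all subjects have completed the study.
- The protocol expects some long courses. Section 4.5.1 speaks of corticosteroids for more than 4 weeks, and 4.5.4.1 of prolonged steroid tapers.
- Protocol Table 5.1-3 marks review of concomitant medication for follow-up visits X01 and X02 only, and X02 falls 100-114 days after the last dose.

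Long courses are the most likely to be open, and they belong to the events that are hardest to control. At one data cut, an unresolved event would be censored while the steroid course given for it would have no censoring rule. At stake is a descriptive secondary result on how long IMAEs need treatment. No test or decision rule depends on it.

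**Working it through.** The plan states no figure for medication duration, so there is none to reproduce. The check asks what plain statistics do to a mean and a median when a fraction *f* of courses is open.

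**Inputs**
- From the documents: 150 treated subjects and a planning rate of 13% for grade 3-5 IMAEs (Protocol 8.1). 0.13 × 150 = 19.5, so about 20 subjects; one open course among 20 is 5%.
- Assumed, because the documents give neither: *f* from 5% to 40%, and a true median of 60 days. The percentage shortfalls below do not depend on the 60.

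**1. Exponential durations, random (exponential) censoring.** Let durations have rate λ = ln 2 / 60, so the true mean is 60 / ln 2 = 86.6 days. Let censoring have rate c.
- Fraction open: *f* = c / (λ + c).
- An open course cut at its length so far gives min(T, C), which is exponential with rate λ + c. Mean and median are both multiplied by λ / (λ + c) = 1 − *f*.
- If open courses are dropped, the remaining durations follow the same distribution, so the factor is again 1 − *f*.

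| Fraction open | Plain median (days) | Plain mean (days) | Kaplan-Meier median (days) |
|---|---|---|---|
| 5% | 57 | 82 | 60 |
| 10% | 54 | 78 | 60 |
| 20% | 48 | 69 | 60 |
| 30% | 42 | 61 | 60 |
| 40% | 36 | 52 | 60 |

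A simulation with 400,000 draws gave the same values.

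**2. Exponential durations, all open courses cut late at one time.** The cut is at q = −ln(*f*) / λ, which lies beyond the median for every *f* used.
- Cut short: the median stays at 60. The mean is (1 − *f*) / λ, which is 82, 69 and 52 days at 5, 20 and 40% open.
- Dropped: the median is −ln((1 + *f*) / 2) / λ, which is 56, 44 and 31 days. The mean is 1/λ − q*f* / (1 − *f*), which is 73, 52 and 34 days.

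**3. Less dispersed durations (Weibull), random censoring, open courses cut short.** By simulation, the shortfall of mean and median is:

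| Weibull shape | 20% open | 40% open |
|---|---|---|
| 1 (exponential) | 20% | 40% |
| 2 | 13-14% | 27-31% |
| 3 | 11-12% | 24-25% |

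Dropping open courses also biases both statistics low, but by less for shapes 2 and 3: about 6-7% at shape 2 with 20% open.

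**Result.** The mean is too low under either simple handling in every case. The median is too low except when open courses are cut beyond it and kept in. The one-to-one link between shortfall and fraction open holds for the exponential case with random censoring, not in general.

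**The case against.** **The SAP does not say that open courses count as finished.** A reader might infer this from the words summary statistics, but the text is silent. Missing and partial medication dates go to an external specification, and the full list of analyses goes to a Data Presentation Plan; neither is available. This stands: the fault is an absent rule, not a stated wrong one. Still, nothing in the SAP itself censors an open course or reports how many were open.

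**The term might cover a Kaplan-Meier median.** SAP 7.6.8.3 lists a Kaplan-Meier median under a heading of summary statistics, and the SAP uses Kaplan-Meier for more than the three endpoints named in 7.1. But where it does so it says so. SAP 7.4.1 marks number of doses as summary statistics and, in the same list, specifies a censored curve for treatment duration. The 7.1 default is the more natural reading of 7.6.8.4.

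**The final analysis may be little affected.** Treatment is capped at 24 months, and the final analysis follows the last subject's opportunity for five years of follow-up. Protocol 5.3.2 asks for concomitant medications to be recorded throughout the study, so stop dates after X02 may be captured even though Table 5.1-3 schedules no later review. This largely stands, and it places the concern mainly at the publication cuts.

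**Persistent events are not hidden.** Time to resolution is censored properly, the percentage resolved is reported, and medications are listed by subject. True, but none of these estimates how long medication was needed.

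**Kaplan-Meier is not a clean remedy.** The endpoint totals all medications for an event, so a single stop is undefined until the SAP defines it. A subject between two courses at the cut looks stopped but may restart, which can leave even Kaplan-Meier somewhat low. SAP 7.6.8.4 also reports by category and treatment group, and Protocol Table 6.2.2-1 has ten categories; about 20 grade 3-5 subjects will not support a median in most cells. Both points stand and shape the fix.

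**Conclusion.** The concern holds as an estimator that does not suit the data together with a missing rule. If any courses are open, the plain mean is too low whether they are cut short or dropped. The median is also too low if they are dropped, or cut before the median. This assumes that censoring is unrelated to course length other than through longer courses being more often caught open.

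The size cannot be derived from the documents. With an assumed 5-40% ongoing, the shortfall is about 5-40% for exponential durations under random censoring, and less for tighter distributions. A reader might infer that reported durations will be understated by some fixed percentage. The documents do not support that: they give neither the fraction open nor the distribution, and late censoring can leave the median untouched.

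The effect is probably largest at publication cuts and small at the five-year analysis if stop dates continue to be collected. This is a worthwhile and cheap improvement to a descriptive secondary result. It does not touch the primary endpoint.

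**What to change.** In SAP 7.6.2 and 7.6.8.4, and in the parallel lines of 7.6.10.4 and 7.6.11.4:

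1. Report the number and percentage of courses ongoing beside every duration summary.
2. For all treated subjects with an IMAE (any grade, and grade 3-5), give the Kaplan-Meier median duration with 95% CI.
3. Define total duration as first start to final stop of immune-modulating medication for the event. Count death on medication as a stop. Censor ongoing courses at the last date the subject is known to be on medication. For high-dose and taper durations, use the start and end of that phase.
4. State how a course that runs past the 100-day window is treated.
5. Where category or group cells are too small for a Kaplan-Meier median, keep the descriptive statistics and flag the ongoing courses.

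The cost is SAP wording and slightly more analysis work, with a method the SAP already uses elsewhere and no new data or visits. The downside is wide intervals with about 20 expected grade 3-5 subjects. The first-start-to-final-stop definition also includes any gaps between courses, which the table footnote should say.
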